Protocolo: IBMS-SPB

Title: Serratus plane block impact on pain and opioids requirements in breast surgery

EudraCT: 2015-005773-21

Ed. 1.1, February 19th, 2016

Official title

Serratus plane block impact on pain and opioids requirements in breast surgery.

Brief summary

The purpose of this project is to evaluate the analgesic efficacy of a regional anesthesia technique (interfascial block at the serratus muscle) performed in patient undergoing breast surgery and the effect of this technique on postoperative analgesia.

Final version of the protocol: #3 18/06/2015. Approved by Hospital la Fe review Board 30/06/2016. NCT02905149.

Detailed description

Regional analgesia techniques have shown to have benefits over conventional analgesia. The lower opioids analgesics requirements decrease side effects associated with the use of this type of medication.

It is also increasingly established scientific evidence that reducing opioids administration may play a role in prognosis of cancer patients given the immunosuppressive effect of these drugs.

In patients undergoing oncologic/reconstructive breast surgery paravertebral block has been traditionally performed, however the paravertebral space lacks a clear anatomical barrier from the spinal cord so the drugs administered can diffuse to the intervertebral foramen causing deeper levels of blocks (epidural or spinal blocks) and injections at the paravertebral level are associated with serious complications both neurological and respiratory (meningitis, spinal hematomas abscesses, pneumothorax, respiratory failure. This has led to the development of less invasive technique with an improved safety profile.

The serratus plane block falls within the framework of these newly developed techniques and the present study aims to assess its role in the management of the patient undergoing cancer / reconstructive surgery.

Methods

Inclusion criteria: (A) patients ≥ 18 years old; (B) American Society of Anesthesiologists (ASA) risk scale $< IV$; and (C) oncologic breast surgery, with or without reconstruction, with at least 24 hours' hospital stay (eg, mastectomy or partial mastectomy, also known as lumpectomy, with axillary regional or radical lymph node dissection).

Exclusion criteria: (A) patients with ASA risk scale $\geq IV$; (B) body mass index (BMI) > 40 ; (C) neurologic impairment; (D) inability to give informed consent; (E) contraindications to nerve block, such as coagulopathy and local infection at the site of the block; (F) local anesthetic allergy; and (G) chronic opioid treatment. Before surgery, all participants receive education regarding the visual analog scale (VAS) pain score (0 mm=no pain and 100 mm=worst imaginable pain) and the use of electronic patient-controlled analgesia (PCA) pumps. After performing standard monitoring with pulse oximeter, ECG, non-invasive blood pressure (GE

Healthcare, Chicago, Illinois, USA), bispectral index module (BIS module, GE Healthcare, Helsinki, Finland), and TOF-Watch-S (Organon Teknika, Oss, The Netherlands), general anesthesia is induced with intravenous midazolam 0.01–0.03 mg/kg, fentanyl 1 µg/kg, and propofol 2 mg/kg. A laryngeal mask is introduced after the administration of intravenous rocuronium bromide 0.6 mg/kg for muscle relaxation. The lungs are ventilated to maintain an end-tidal carbon dioxide of 35 mm Hg. Anesthesia is maintained with an oxygen fraction (FiO₂) of 0.4 and propofol continuous intravenous infusion to keep BIS index between 40 and 60. After anesthesia induction, patients are randomly allocated into two groups (1:1 allocation ratio) by a random sequence generated from a pseudorandom number seed (!RNDSEQ V.2011.09.0, JMDomenech); these sequences is kept in sealed and consecutively numbered opaque envelopes, which are opened after informed consent is obtained. Patients in the study group receive SPB with the midaxillary line approach, using levobupivacaine 0.25% 30 mL, while those in the control group do not. An anesthetist with experience in interfascial blocks perform the US-guided technique using a linear probe (8–13 MHz), a US machine (M-Turbo, SonoSite, Bothell, Washington, USA), and a 22 G, 50 mm echogenic needle (Stimuplex D; B Braun, Melsungen, Germany). With the patient lying supine and the arm abducted at 90°, the US probe is positioned in a sagittal plane at the midaxillary line. The fascial plane between the serratus anterior muscle and external intercostal muscles is identified between the fourth and fifth ribs in the midaxillary region. The gauge is advanced in-plane, and the local anesthetic is placed by hydrodissecting the interfascial space in a caudal to cranial fashion. Following the initial bolus of fentanyl during induction, perioperative analgesia is achieved by administering a bolus of 1 µg/kg fentanyl if blood pressure and/or heart rate increased $\geq 20\%$ from baseline measurement (first operating room assessment). Thirty minutes before the end of surgery, intravenous paracetamol 1 g is administered in both groups. At the end of surgery, intravenous granisetron 40 µg/kg and dexamethasone 4 mg is administered; muscle relaxation is reversed if needed. During the postoperative period, all patients receive intravenous opioid medication on demand via an electronic PCA pump (CADD Solis, Smiths Medical, Minneapolis, Minnesota, USA). The pump is set to deliver a bolus dose of 1 mg, with a lockout interval of 10 min, and maximum dose of 6 mg/hour without continuous perfusion. The patient is instructed to press the PCA button whenever pain increased to VAS ≥ 40 mm. Moreover, intravenous paracetamol 1 g/8 hours and dexketoprofen 50 mg/8 hours is administered in both groups, as part of multimodal analgesia management.

Recorded data age, BMI, type, site and duration of surgery, type of lymphadenectomy (radical vs regional/sentinel lymph node), intraoperative fentanyl (µg), postoperative morphine (mg), and time-to-opioid first rescue dose. First 24 hours' total opioid requirements (intraoperative+postoperative, primary outcome) were calculated by converting fentanyl used intraoperatively into morphine equivalents (fentanyl conversion factor; 10 µg fentanyl=1 mg morphine). The participants are blinded to group allocation, as the blocks were performed after induction of general anesthesia. The healthcare provider (attending anesthesiologist) who administer the opioid was blinded to subject allocation as he is not present in the operating room during the standard time used by the investigator to perform the block, even for control subjects who do not receive any block. When attending anesthesiologist is called back to the operating room, the same equipment was present (US machine and disposable items needed to perform the technique, such as syringes and vials) and a white dressing that prevented injection identification is placed on all subjects. In the postoperative period, pain is

assessed by the VAS at 1, 3, 6, 12, and 24 hours after surgery. The occurrence of side effects (nausea, pruritus, apnea, urinary retention, or paralytic ileus), block-related complications, and Pain Out questionnaire answers is recorded at 24 hours after surgery. The data collector for the postoperative data is a different investigator from the one who performed the block and was blinded to the subjects' study group allocation.

The study has planned data monitoring and auditing by the IIS la Fe according to AEMPS guidelines. Consistency will be checked during analysis phase with Stata statistical software. Registries will be obtained from electronic medical records available for double check procedures. All variables are obtained from the subject electronic medical record.

Sample size: Considering a decrease in postoperative morphine consumption of 40% and the average consumption of opioid after breast surgery under general anesthesia is 15 milligrams (standard deviation 8 mg) we calculated that , with an alpha error 5% power 80 % 56 patients (28 per group) were required to achieve a significant result. In anticipation of possible loss of sample , 60 patients were recruited . Analysis will be performed by intention to treat.

Statistical Analysis Plan

Continuous variables were reported as medians with IQRs or means with SDs where applicable; categorical variables were reported as counts and percentages. We checked for the normality of continuous variables by using the Shapiro-Wilk test.

Quantitative variables (opioid consumption , pain estimated by VAS scale) will be analyzed using mixed linear model adding a random variable for interindividual variability for pain threshold. If the data do not meet the criteria of normality the Mann-Whitney U test will be used. If the groups differ in preoperative variables., We will make a multivariable analysis adjusting for these variables. The need for rescue analgesia over time is analyzed by Kaplan-Meier curve where the terminal state is the administration of the first dose of opioid postoperatively. The difference side effects (nausea , pruritus , apnea , urinary retention, ileus) and complications IPO questionnaire and analyzed by chi-square test and Fisher exact test. Scheffe correction will be applied for multiple comparison. Missing data are excluded from analysis.

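### Body weight drives part of the spread in the mg primary outcome, including a dose given before allocation; weight should be a prespecified covariate

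*Combined protocol and SAP*

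**What the plan says.** All references are to the combined protocol and SAP.

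- **Induction (Methods).** "general anesthesia is induced with intravenous midazolam 0.01–0.03 mg/kg, fentanyl 1 µg/kg, and propofol 2 mg/kg". Every patient receives this fentanyl dose.
- **Allocation (Methods).** "After anesthesia induction, patients are randomly allocated into two groups". The block, or no block, follows.
- **Later intraoperative fentanyl (Methods).** "Following the initial bolus of fentanyl during induction, perioperative analgesia is achieved by administering a bolus of" the same per-kg size, triggered by a rise in blood pressure or heart rate.
- **Primary outcome (Methods, recorded data).** "First 24 hours' total opioid requirements (intraoperative+postoperative, primary outcome) were calculated by converting fentanyl used intraoperatively into morphine equivalents", with the factor given as "fentanyl conversion factor; 10 µg fentanyl=1 mg morphine". Nothing takes the induction dose out of the total.
- **Recorded variables (Methods).** The list begins "Recorded data age, BMI, type, site and duration of surgery". Intraoperative fentanyl appears as one amount. BMI is listed; weight and height are not.
- **Sample size.** A 40% fall in postoperative morphine from a mean of 15 mg (SD 8 mg), alpha 5%, power 80%, gives 28 per group; 60 patients allow for losses.
- **Statistical Analysis Plan.** Opioid consumption is compared by a mixed linear model, or by Mann-Whitney U if normality fails. Multivariable adjustment is made only if the groups differ on preoperative variables.

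**The concern.** The induction dose is fixed by body weight before the patient has a group, so it carries no information about the block. At the plan's conversion factor it adds 0.1 mg of morphine equivalent per kg to the outcome. Each triggered bolus adds another 0.1 mg per kg, so a heavier patient scores more mg for the same number of boluses.

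This weight-driven part of the outcome is noise in a comparison of group means. It could be removed with a baseline variable that the anaesthetist must already know in order to dose. As written, the plan uses weight only if the groups happen to differ on it. That misses the main reason to adjust for a prognostic baseline variable, which is precision whether or not there is imbalance. It also makes the choice of model depend on the data.

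What is at stake is a modest amount of precision in a 60-patient trial, not the validity of the comparison.

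**Working it through.** **1. The plan's own figure.** Difference = 0.40 × 15 = 6 mg; SD 8 mg; two-sided 5%; power 80%.

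n per group = 2 × (1.960 + 0.842)² × 8² / 6² = 27.9, so 28. The stated 28 per group (56 in total) is reproduced. Normal-approximation power is 80.1% at 28 per group and 82.8% at 30.

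**2. Size of the induction dose.** 1 µg/kg ÷ 10 µg per mg = 0.1 mg per kg. The documents give no weights. At an assumed 50, 70 or 90 kg this is 5, 7 or 9 mg, with the same expected amount in both groups.

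**3. Model for the spread.** Let W be weight, K the number of triggered boluses and M postoperative morphine:

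Y = 0.1 × W × (1 + K) + M

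From the document: the factor 0.1 and SD(M) = 8. Assumed: W has mean 70 kg and SD 13 kg; K is Poisson with mean λ; W, K and M are independent. Then E(W²) = 70² + 13² = 5069, and

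- Var(Y) = 64 + 0.01 × [5069 × (λ + (1 + λ)²) − 4900 × (1 + λ)²]
- variance explained by a linear weight term = (0.1 × (1 + λ))² × 169

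| λ | Var(Y) | Explained by weight | Share removed | SD before → after |
|---|---|---|---|---|
| 0 | 65.69 | 1.69 | 2.6% | 8.10 → 8.00 |
| 1 | 121.45 | 6.76 | 5.6% | 11.02 → 10.71 |
| 2 | 180.59 | 15.21 | 8.4% | 13.44 → 12.86 |

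**4. Power.** For a 6 mg difference at 30 per group, power = Φ(6 / (SD × √(2/30)) − 1.96):

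- λ = 0: 81.8% → 82.8%
- λ = 1: 55.9% → 58.3%
- λ = 2: 40.9% → 43.9%

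The gain is 1.0, 2.4 and 3.0 points. In patients, 60 × (Var before / Var after) − 60 = 1.6, 3.5 and 5.5. The absolute power levels for λ = 1 and 2 should not be read as a forecast: they hold the difference at 6 mg, as if the block had no effect on triggered boluses.

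**5. Covariate or redefinition?** Dropping the induction dose without adjusting leaves Y − 0.1W, with variance 64.00, 116.38 and 172.14. That is a cut of 2.6%, 4.2% and 4.7%. The weight covariate alone gives the full 2.6%, 5.6% and 8.4%. Because the induction dose is exactly linear in weight, a linear weight term absorbs it, and the adjusted group difference is the same with or without the dose in the outcome.

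**6. Sensitivity to independence.** Take λ = 0, weight SD 12 kg, and correlation ρ between weight and other opioid use. Var(Y) = 64 + 1.44 + 2ρ × 8 × 1.2; after adjustment it is 64 × (1 − ρ²).

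| ρ | Var(Y) | After adjustment | Share removed | Unadjusted power, 28 per group |
|---|---|---|---|---|
| −0.3 | 59.68 | 58.24 | 2.4% | 82.8% |
| 0 | 65.44 | 64.00 | 2.2% | 79.3% |
| 0.3 | 71.20 | 58.24 | 18.2% | 75.8% |

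The covariate does not increase the residual variance in any of these cases. At ρ = −0.3, dropping the dose without adjusting would raise the variance, from 59.68 to 64.

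**The case against.** **The induction dose dilutes the planned effect.** A reader might infer this, since at 70 kg a 6 mg saving is 6/15 = 40% without the dose and 6/22 = 27% with it. The documents do not support it as a flaw. No percentage analysis is planned. The 40% is stated for postoperative morphine, not for the total. A dose with the same expected amount in both groups leaves the 6 mg mean difference unbiased. Nor would dropping the dose restore the 40% scale: one triggered bolus on average at 70 kg puts the control mean back to 15 + 7 = 22 mg. That the sample size uses postoperative inputs for a total-opioid outcome is a separate matter.

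**The primary outcome should be replaced by post-allocation opioid.** This is also tempting, but it is a debatable trade. The Detailed description motivates the trial by opioid side effects and immunosuppression, for which total exposure is a defensible measure. Under the linear model the weight covariate does all the work.

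**The gain is small and rests on assumed weights and bolus counts.** This stands. Recruiting 60 rather than 56 covers the induction-dose noise taken alone if few patients are lost: with no correlation, power at 30 per group is 80.5 to 82.4% for weight SDs of 20 down to 8 kg.

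**Weight is obtainable anyway.** This also stands, since per-kg dosing needs it and the variables come from the electronic record. It makes the fix cheap but does not prespecify the covariate.

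**The plan never says outright that the induction dose counts.** True. It is the natural reading, because the later boluses are described as following an initial one, but one sentence should settle it.

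**Conclusion.** The point holds as a low-cost gain in precision. The primary outcome, as naturally read, contains a pre-allocation dose and later boluses that all scale with weight, and the plan uses weight only if the groups differ. There is no bias, no invalid test and no error in the stated sample size.

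The avoidable variance is about 2.6% to 8.4% of the total, or about 1 to 3 power points, for an average of 0 to 2 triggered boluses. These figures assume 70 kg, SD 13 kg, Poisson bolus counts and no link between weight and postoperative morphine. A positive link would make the gain larger. With a negative link it can shrink to nothing: at weight SD 12 kg and no triggered boluses, the weight slope is zero when ρ = −1.2/8 = −0.15. The documents give no data on any of these inputs.

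**What to change.** 1. Add body weight to the recorded variables, taken from the medical record, and prespecify it as a covariate in the linear model for the primary outcome, whether or not the groups differ on it.
2. Keep total 24-hour opioid as the primary outcome, and state in one sentence that the induction dose is included.
3. Record the induction fentanyl separately from later intraoperative fentanyl.
4. Prespecify opioid given after allocation (later fentanyl converted, plus postoperative morphine to 24 hours) as a supportive analysis. Mann-Whitney U cannot take a covariate, so if that fallback is used this analysis still takes the induction-dose noise out.

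Cost: one covariate (one degree of freedom among about 60 patients), one extra recorded variable with the induction dose split out, and a few sentences of text. The anaesthetic regimen is unaffected.

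### The 80% power was calculated for postoperative morphine, but the primary outcome is total 24-hour opioid, so power for the primary test is not established

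*Combined protocol and SAP*

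**What the plan says.** In Methods, the paragraph on recorded data names the primary outcome as the first 24 hours' "total opioid requirements (intraoperative+postoperative, primary outcome"), with intraoperative fentanyl converted to morphine at 10 µg to 1 mg. The same paragraph lists intraoperative fentanyl as one recorded item and "postoperative morphine (mg), and time-to-opioid first rescue dose" as others, so the two components are available separately.

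The sample-size paragraph that follows uses another variable. It starts "Considering a decrease in postoperative morphine consumption of 40" per cent, assumes that "the average consumption of opioid after breast surgery under general anesthesia is 15 milligrams (standard deviation 8 mg"), and concludes that "with an alpha error 5% power 80 % 56 patients (28 per group) were required". It then adds: "In anticipation of possible loss of sample , 60 patients were recruited".

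The Statistical Analysis Plan says "Quantitative variables (opioid consumption , pain estimated by VAS scale) will be analyzed using mixed linear model". It does not say which opioid variable is meant and contains no power statement.

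**The concern.** The variable that was sized is one component of the primary outcome, and no planning figure carries the calculation from the component to the sum. A reader will nevertheless take 80% as the power of the primary comparison.

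The part left out is not small. Methods gives fentanyl in boluses of 1 µg/kg: one at induction, then more whenever blood pressure or heart rate rises by at least 20%. At the plan's own conversion each bolus counts as 0.1 mg/kg morphine, or 7 mg at an assumed 70 kg. One extra bolus therefore outweighs the whole 6 mg difference on which the trial was sized, and the number of boluses will vary between patients.

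What is at stake is how the primary result is read, above all a non-significant one: the plan does not show that the trial had an 80% chance of detecting the effect it was designed around.

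**Working it through.** **Inputs from the documents.** Postoperative mean 15 mg, SD 8 mg, 40% reduction, alpha 5%, power 80%, 28 per group, 60 recruited (30 per group at 1:1), 10 µg fentanyl = 1 mg morphine, boluses of 1 µg/kg. Sidedness is not stated; two-sided reproduces the plan's number and one-sided does not (22 per group).

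**Step 1: the plan's own figure.** Difference = 0.40 × 15 = 6 mg. Then n = 2(1.960 + 0.842)² × (8/6)² = 27.9, so 28 per group. The arithmetic is right for postoperative morphine. By the noncentral t distribution, used for power below, 28 per arm gives 78.7% and 30 per arm 81.5%.

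**Step 2: variance added, no intraoperative effect.** The documents give no intraoperative SD, so a range is assumed, independent of postoperative use. SD of total = √(8² + SD_intraop²), with the difference held at 6 mg. The last two columns give the extra intraoperative difference that would restore 80% power.

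| Assumed intraop SD (mg) | SD of total (mg) | Power, 28 per arm | Power, 30 per arm | Extra needed, 28 per arm (mg) | Extra needed, 30 per arm (mg) |
|---|---|---|---|---|---|
| 0 | 8.00 | 79% | 82% | – | – |
| 4 | 8.94 | 69% | 72% | 0.8 | 0.6 |
| 8 | 11.31 | 50% | 52% | 2.6 | 2.3 |
| 12 | 14.42 | 33% | 35% | 5.0 | 4.6 |

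Correlation between the components also matters. By the normal approximation at 28 per arm, power for SD 4/8/12 mg is 71/51/34% at zero correlation and 62/41/28% at a correlation of 0.3. Negative correlation would raise it.

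**Step 3: a bolus model that allows an intraoperative saving.** Assumptions: weight 70 kg (SD 12), one induction bolus, Poisson extra boluses with control mean 1, 2 or 3, and postoperative use as in the plan. The intraoperative amount is K·W/10 mg, where K is the number of boluses and W the weight. Its control-arm variance is (E[K]²·Var W + E[W]²·Var K + Var K·Var W)/100. For a mean of one extra bolus that is (4 × 144 + 4900 × 1 + 1 × 144)/100 = 56.2, an SD of 7.5 mg, so the SD range in Step 2 is not extreme. Simulated power (40,000 trials per cell, two-sided t test):

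| Fall in extra boluses | 28 per arm (mean 1/2/3) | 30 per arm (mean 1/2/3) |
|---|---|---|
| none | 52/38/30% | 55/41/31% |
| 20% | about 71–72% | about 74–75% |
| 40% | 87/93/96% | 90/95/97% |

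Reaching 80% needs the extra boluses to fall by about 25–29% at 28 per arm, or 23–26% at 30 per arm. Assuming 60 or 80 kg instead, at 28 per arm, gives 57/44/35% or 47/33/26% with no fall, and still 87–96% with a 40% fall.

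**Step 4: the induction bolus alone.** Its SD is 12 kg × 1 µg/kg ÷ 10 = 1.2 mg, so the SD of the total is √(64 + 1.44) = 8.09 mg and power at 28 per arm moves only from 78.7% to 77.8%. It leaves the 6 mg difference unchanged but alters its relative size: 15 to 9 mg (40%) becomes 22 to 16 mg (6/22 = 27%).

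**The case against.** The best defence is that the block is placed before the boluses triggered by haemodynamic response, so some intraoperative saving is a natural expectation. If the plan's own 40% applied to those boluses as well, power would exceed 80%. The low figures need a block that cuts postoperative morphine by 40% and leaves intraoperative fentanyl unchanged. Moreover, every departure from 80% rests on inputs that the documents do not contain.

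Much of this stands. It rules out any claim that the trial is underpowered, and the numbers above illustrate a range without estimating the true power. It does not rescue the stated 80%, because the plan assumes no intraoperative effect anywhere, and in the bolus model a 20% fall still leaves power below 80% at both 28 and 30 per arm. A defence that the calculation is conservative depends on an assumption the plan does not make.

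Two narrower points also have force. The outcomes are related by definition, since one is part of the other; what is missing is a planning figure for the sum. And a null result is read mainly from its estimate and confidence interval, which do not depend on planning power. The consequence is that 80% should not be quoted for the primary test, not that the result would be uninterpretable.

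The rise to 60 patients does not settle the matter. The extra four are there to cover losses, and with all 60 analysed and no intraoperative saving, power is 72% at an intraoperative SD of 4 mg and 52% at 8 mg.

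**Conclusion.** The concern holds. The 28 per group is correct for a 6 mg difference in postoperative morphine with SD 8 mg, and the plan gives no basis for applying the same 80% to total 24-hour opioid. That mismatch is certain from the text. The direction and size of the effect on power are not known: across the scenarios at 70 kg and 28 per arm, power runs from about 30% with no intraoperative saving to 96% with a 40% fall in extra boluses. All of these rest on assumed intraoperative variability, bolus counts, body weight and effect. This should be fixed, because 80% is the only power the plan states and it belongs to a variable other than the primary outcome.

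**What to change.** Keep the declared primary outcome. In the sample-size paragraph:

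- State that 80% power and 28 per group apply to postoperative morphine only.
- Give the assumed mean, SD and difference for total 24-hour morphine equivalents, and the power that 56 to 60 patients provide for it. If no data exist, give a range with its assumptions, or say plainly that power for the total was not calculated.

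It would also help to report intraoperative fentanyl and postoperative morphine beside the total, since both are already recorded. As a clarification only, say whether the induction fentanyl is counted in the total, because allocation follows induction ("After anesthesia induction, patients are randomly allocated into two groups") and the block cannot change that dose.

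The cost is a few sentences and one re-run calculation, with no extra patients, no new data and no change of outcome. The drawback is that the power stated for the primary outcome may be less favourable than 80%, or may have to be a wide range.

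### VAS model with one patient term: if pain spread changes between 1 and 24 hours, intervals at single times are miscalibrated; specify an unstructured covariance

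*Combined protocol and SAP*

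**What the plan says.** The Statistical Analysis Plan treats opioid consumption and VAS together: both go into a linear mixed model, "adding a random variable for interindividual variability for pain threshold". It names no residual covariance, time term, arm-by-time term or robust standard error.

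Under Methods (recorded data), pain is "assessed by the VAS at 1, 3, 6, 12, and 24 hours after surgery", so each patient gives five unequally spaced readings.

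Three further SAP sentences bear on the point:

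- Normality and the fallback: "We checked for the normality of continuous variables by using the Shapiro-Wilk test", and "If the data do not meet the criteria of normality the Mann-Whitney U test will be used".
- Multiplicity: "Scheffe correction will be applied for multiple comparison". The comparisons it covers are not listed.
- Missing values: "Missing data are excluded from analysis".

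The primary outcome is "First 24 hours' total opioid requirements (intraoperative+postoperative, primary outcome"), one value per patient. VAS is therefore secondary. The documents give no VAS SD or correlation.

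**The concern.** One random term per patient with independent, equal-variance residuals is compound symmetry. Readings 2 hours apart and 23 hours apart get the same correlation, and 1 h and 24 h get the same variance. Constancy is not a safe assumption here. The early readings fall soon after a single injection, while patient-controlled analgesia is starting. By 24 h there has been a day of pain-triggered and scheduled dosing. The documents do not show which way the spread moves.

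If it does move, a standard error built from the pooled variance is wrong at individual times. The early hours, where a single-shot block would be expected to show its effect, would then be reported with too much or too little certainty. A larger critical value does not repair this, because it stretches every interval by the same factor.

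**Working it through.** **The plan's own figure.** The only sample-size calculation is for opioid use: difference 40% of 15 mg = 6 mg, SD 8 mg. Then n per group = 2 × (1.960 + 0.842)² × 8² / 6² = 27.9, so 28 per group and 56 in all. It reproduces (two-sided 5%, normal approximation). It uses one value per patient and does not depend on any VAS covariance.

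**Inputs for VAS.** Five times (Methods); 60 patients allocated 1:1, taken as 30 per arm with complete data. The SD profiles are assumptions.

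**Formula.** With complete data and separate arm means at each time, the random-intercept model estimates the total variance as the mean of the five per-time variances. So

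- model SE = RMS(SD) × √(2/n) at every time;
- true SE at time t = SD_t × √(2/n);
- ratio = RMS(SD) / SD_t.

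The correlation does not enter the single-time ratio.

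**Worked case, SDs 22, 20, 18, 16, 14 mm.** Sum of squares 484 + 400 + 324 + 256 + 196 = 1,660; mean 332; RMS 18.22. With √(2/30) = 0.2582, model SE = 4.70 mm at every time. True SE is 5.68 mm at 1 h and 3.61 mm at 24 h. The ratios are 18.22/22 = 0.83 (17% too narrow) and 18.22/14 = 1.30 (30% too wide).

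**Range of assumptions** (nominal 5% two-sided test, 58 df, no multiplicity correction):

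| SDs at 1, 3, 6, 12, 24 h (mm) | ratio 1 h | ratio 24 h | type I error 1 h | type I error 24 h |
|---|---|---|---|---|
| equal | 1.00 | 1.00 | 5% | 5% |
| 20, 19, 18, 17, 16 | 0.90 | 1.13 | 7.6% | 2.8% |
| 22, 20, 18, 16, 14 | 0.83 | 1.30 | 10.3% | 1.2% |
| 25, 22, 20, 16, 12 | 0.78 | 1.63 | 12.3% | 0.2% |

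If spread grows instead of shrinking, the pattern reverses. Simulation of the 22-to-14 case (20,000 trials, 30 per arm) agrees: about 10% at 1 h and 1% at 24 h, against about 5% at every time when each time's own variance is used. The time-averaged arm effect stays at about 5%.

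**Correlation alone.** With equal SDs and correlation that decays over time, single-time tests hold 5%, but the arm-by-time F test rejects about 6-8%, against 4.7-5.5% with an unstructured covariance. With correlation 0.8 per visit (28 per arm), the test of change in arm difference from 1 h to 3 h rejects 1.0% and from 1 h to 24 h 14.0%.

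**Under Scheffe.** If the correction covers the VAS times, the critical value is √(4 × F₀.₉₅(4, 58)) = 3.18, or 3.45 with 5 numerator df. For the 22-to-14 and 25-to-12 profiles the chance of any false positive over the five times was then at most 2.1%.

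Power is a different matter. Take an assumed 12 mm true difference at 24 h, SDs 22 to 14, and the large-sample critical value √9.49 = 3.08:

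- own variance: Φ(12/3.615 − 3.08) = Φ(0.24) = 59%;
- pooled variance: Φ((12 − 3.08 × 4.705)/3.615) = Φ(−0.69) = 25%.

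With 3.18 in place of 3.08 the figures are about 56% and 21%.

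**The case against.** The strongest case against has five parts.

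1. **The text does not impose compound symmetry.** A reader might infer that the SAP forces equal variance and correlation. It does not: a random intercept can be combined with heterogeneous or correlated residuals, and the SAP is silent on residuals. This stands. Compound symmetry is the default reading only. Silence still leaves the structure to be chosen after the data are seen.

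2. **The harm is conditional.** With equal SDs there is no single-time error, and the documents give no VAS SDs. This stands, and every figure above except the sample-size check rests on an assumed profile.

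3. **Single-time comparisons are not listed.** They are inferred from two features. A Scheffe correction has little use in a two-arm trial without several contrasts. The Mann-Whitney fallback takes one value per patient, and no VAS summary is defined. The Scheffe sentence follows the one on side effects and the questionnaire, so other readings are possible. The inference is reasonable but not certain.

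4. **Scheffe removes the false positives.** A reader might infer from the 10% and 12% figures that the trial would declare spurious early pain benefits. Those are unadjusted rates. Under the planned correction, if it covers these tests, the chance of any false positive is about 2%. This stands, but the uneven intervals and the lost power remain.

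5. **VAS may never reach this model.** VAS is bounded, may fail the Shapiro-Wilk check, and would then go to Mann-Whitney. A Mann-Whitney test at one time uses only that time's data, so the problem does not arise there. This stands. The point applies to VAS that stays in the mixed model.

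**Conclusion.** The point holds in conditional form. On the default reading, the VAS model assumes one variance and one correlation from 1 to 24 h. If spread changes over time, intervals for arm differences at single times are too narrow where spread is large and too wide where it is small. That means about 17% and 30% for SDs of 22 to 14 mm, and less or more for the milder and steeper profiles. If correlation decays, an arm-by-time test is mildly liberal (about 6-8%) even with equal SDs.

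A reader might infer that the trial's main conclusion is at risk. The documents do not support that: the primary outcome is a single total per patient, the sample size rests on opioid use, and with complete data the time-averaged VAS effect keeps its 5% error rate. This is a worthwhile, inexpensive improvement to the analysis of a secondary outcome that the study title names.

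**What to change.** Separate VAS from opioid consumption in the SAP. For VAS, specify a repeated-measures linear model with:

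- arm, time (categorical, five levels) and arm-by-time;
- an unstructured within-patient covariance, fitted by REML;
- Kenward-Roger or Satterthwaite degrees of freedom;
- a stated fallback if it does not converge: heterogeneous variances with a correlation that decays with time (heterogeneous Toeplitz or spatial power), then robust standard errors.

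Take the overall arm difference and the difference at each time, with 95% CIs, from this one model. State which of these comparisons the Scheffe correction covers.

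The cost is a paragraph of SAP text and a change of model option, with no extra data. The small downside is 15 covariance parameters (5 variances + 10 covariances) instead of 2, which 60 patients with five readings each can support. Using each time's own variance brought single-time type I error back to about 5% in every profile tested.
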